- 7. The subject's systolic blood pressure is ≥ 100 and ≤ 155 mmHg, diastolic blood pressure is ≥ 40 and ≤ 95 mmHg, and heart rate is ≥ 45 and ≤ 100 bpm (taken sitting or supine). Any recorded values outside of these ranges and assessed by the Investigator to be not

clinically significant must be reviewed with the Sponsor Medical Monitor for approval prior to enrollment.

- 8. The subject has no clinically significant abnormality of serum hemoglobin, hematocrit, white blood cells, and platelets, or usual serum biochemistry: electrolytes, renal function, liver function and serum proteins that might be expected to interfere with the subject's health and/or medical treatment during the study.
- 9. In subjects who have partners of childbearing potential, the subject and his partner should abstain from sexual intercourse, or use highly effective contraceptive measures (e.g., oral contraceptive and condom, intrauterine device [IUD] and condom, or diaphragm with spermicide and condoms; other forms of contraception must be approved by the Medical Monitor) when engaging in sexual intercourse throughout the study, and for at least 90 days after the last dose of abaloparatide.
- 10. The subject has read, understood, and signed the written informed consent form (ICF).

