## 4.5.7 Vital Signs and Physical Examination

The actual value, the change from baseline to each visit, the change from baseline to the worst post-baseline value during the treatment period, and the change from baseline to Month 13 (Follow-up visit) will be summarized for vital signs using descriptive statistics by treatment group. If a subject has repeat assessments on the vital signs at a particular scheduled visit/time point, the last non-missing value will be used for the by-visit summary. Unscheduled assessments will be included in the summaries for the worst post-baseline value or PCS, they will not be included in the descriptive by-visit summary tables.

The number (%) of subjects experiencing post-dose orthostatic hypotension will be summarized by treatment group, visit and time point, and across all visits. Orthostatic hypotension will be defined as a decrease in systolic blood pressure (SBP) of  $\geq 20$  mmHg from supine to standing or in diastolic blood pressure (DBP) of  $\geq 10$  mmHg supine to standing. Results from unscheduled visits will be included in the summaries.

The number (%) of subjects experiencing heart rate increase from pre-dose to post-dose and the number of occurrences per subject will be summarized with various threshold values (ranging from >5 bpm to >40 bpm, with threshold values increasing by 5 BPM). The median, minimum and maximum heart rate increase (in BPM) will be provided per threshold value. The number of occurrences per subject will be summarized using the median, minimum and maximum values.

All heart rate data, including repeat and unscheduled assessments, will be included in determining the increase from pre-dose in this summary.

Criteria for determining values of vital sign measurements that are considered PCS are in Appendix C of this SAP. The number (%) of subjects who have at least 1 PCS vital sign values for each vital sign parameter of interest after the first dose of study drug, but had no PCS values at baseline, will be presented by treatment. Results from unscheduled visits will be included in identification of subjects with post-baseline PCS values, as applicable. For the calculation of the percentages of subjects, the denominator will be based on the number of subjects who had no PCS values at baseline and had at least one post-baseline assessment for the specific vital sign parameter of interest.

A listing of subjects with any PCS vital sign values will be provided.

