## Appendix B. Criteria for Potentially Clinically Significant Laboratory Values

Parameter	Unit	Lower Criteria	Upper Criteria
Heart Rate	bpm	< 45	>100
			>130
Supine systolic blood pressure	mm Hg	< 80	>155
Supine diastolic blood pressure	mmHg		>100
Standing systolic blood pressure	mmHg	<80	>155
Standing diastolic blood pressure	mmHg		>100
Body temperature	°C		≥39.0

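### The baseline exclusion for potentially clinically significant (PCS) vital signs works per parameter, not per criterion, so the count table misses new values above 130 bpm or below 80 mmHg in men who start above 100 bpm or 155 mmHg

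*SAP*

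**What the plan says.** SAP 4.5.7 defines the PCS table for vital signs by treatment group. The numerator is the number of men with "at least 1 PCS vital sign values for each vital sign parameter of interest after the first dose of study drug, but had no PCS" finding before the first dose. For the percentage, "the denominator will be based on the number of subjects who had no PCS values at baseline and had at least one post-baseline assessment" and this is taken "for the specific vital sign parameter of interest". Neither sentence separates high from low limits, or a milder from a more extreme one.

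The limits are in the vital signs table of Appendix C:

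- Heart rate: "Heart Rate bpm < 45 >100", with a second upper limit of 130 bpm on the next line.
- Supine systolic: "Supine systolic blood pressure mm Hg < 80 >155".
- Standing systolic: "Standing systolic blood pressure mmHg <80 >155".
- Diastolic pressure (supine and standing) and temperature have an upper limit only.

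SAP 3.4 takes baseline as the last non-missing value before the first dose. SAP 4.5.6 uses the same construction for laboratory values: men with a PCS value of that parameter at baseline leave both numerator and denominator.

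**The concern.** The usual purpose of a baseline exclusion is to avoid counting as new an abnormality that was already there. That works when a parameter has one limit. Where limits are opposite or nested, exclusion by parameter goes further. It removes a man from a criterion that he did not meet at baseline and could newly meet on treatment.

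The nested heart rate limits are the clearer problem, because men who start between 100 and 130 bpm are the closest to 130 and are the ones dropped from that row. The opposite systolic limits are less likely to matter but follow the same logic. Tachycardia and orthostatic hypotension are listed as adverse events of special interest in SAP 4.5.3, so a reader will look at these rows.

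**Working it through.** The SAP gives no figure on this point, so there is none to reproduce. The check applies the rule as written to example men and compares it with a rule applied criterion by criterion.

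**Rules.** For a parameter with criteria c1, c2, …:

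- As written: if the baseline value meets any c, the man leaves the numerator and denominator for the whole parameter.
- Per criterion: he leaves the row for c only if his baseline value meets that c.

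**Example men (limits from Appendix C, values illustrative).**

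| Parameter | Baseline → on treatment | As written | Per criterion |
|---|---|---|---|
| Supine systolic | 160 → 75 | excluded | counted under <80 |
| Supine systolic | 150 → 75 | counted under <80 | counted under <80 |
| Heart rate | 105 → 135 | excluded | counted under >130 |
| Heart rate | 95 → 135 | counted under >100 and >130 | counted under >100 and >130 |
| Heart rate | 42 → 135 | excluded | counted under >100 and >130 |

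The two rules differ only for men who meet some limit of that parameter at baseline.

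**Can men start beyond a limit?** Protocol 4.1, criterion 7, caps systolic pressure at 155 mmHg and heart rate at 100 bpm, the same figures as the Appendix C upper limits, so most men start inside. Three routes remain:

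- Values outside the range may be approved before enrollment.
- Baseline is the last pre-dose value, which need not be the one that met entry.
- The entry limits apply to sitting or supine readings, while standing systolic pressure has its own PCS row.

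**How many men.** The documents do not give the share f of men beyond a limit at baseline, so it is an assumption. Men leaving one parameter's table = f × group size.

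| f | Abaloparatide (150) | Placebo (75) |
|---|---|---|
| 1% | 1.5 | 0.75 |
| 5% | 7.5 | 3.75 |
| 10% | 15 | 7.5 |

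Over both arms, 0.02 × 225 = 4.5 and 0.10 × 225 = 22.5, or about 5 to 23 men for f of 2% to 10%.

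**How many events.** Men leaving a denominator are not lost events. To lose a <80 event, a man must fall by more than 155 − 80 = 75 mmHg in the same position. If 1% of the removed men did so (assumption), the loss is 0.01 × 4.5 = 0.045 to 0.01 × 22.5 = 0.225 events over both arms. For >130 bpm the rise needed is smaller, at most about 130 − 100 = 30 bpm for a man who starts above 100, so the proportion could be higher. The documents give nothing from which to estimate it.

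**Do the other outputs give the same count?**

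- Heart rate increase table (4.5.7): 105 to 135 at one visit is +30, which enters the rows from >5 to >25. So does 60 to 90. The table cannot show who passed 130.
- Orthostatic table (4.5.7): it needs a fall on standing of at least 20 systolic or 10 diastolic. A man at 158 supine and 157 standing at baseline, then 78 and 72 after injection, has a systolic fall on standing of 78 − 72 = 6 mmHg. He does not qualify on systolic pressure, and he is excluded from both <80 rows.
- Worst-value change summary (4.5.7): it is descriptive, and the SAP does not say which direction is worst for a two-sided parameter.
- PCS listing (4.5.7): it shows every such man but gives no count by arm.

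**The case against.** The strongest reply is that nothing disappears from the safety report. The listing covers any man with any PCS value. The worst-value summary includes unscheduled readings, the heart rate and orthostatic tables have no baseline exclusion, and 4.5.8 repeats the heart rate table for ECG. Safety is descriptive, and no decision rule uses the PCS table. All of this stands. A reader might infer that the plan conceals worsening, and the documents do not support that. The exclusion also rests on a pre-dose value, so it should fall on both arms alike and does not bias the comparison among the men who remain. What the other outputs do not supply is a count by arm of men newly above 130 bpm or newly below 80 mmHg.

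A second reply is that a programmer might apply the rule by criterion anyway. That is possible, but the SAP does not say so, and its stated unit is the parameter. Supine and standing pressure are separate parameters, so a man who is high only when supine is still assessed for low standing pressure.

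A reader might also take the empty lower cell for diastolic pressure as a defect, to be filled from the entry floor in Protocol 4.1 ("diastolic blood pressure is ≥ 40 and ≤ 95 mmHg"). The documents do not support this either. A one-sided PCS limit is the sponsor's choice; temperature and many laboratory parameters are one-sided too. Of the six distinct heart rate and pressure limits in Appendix C, three equal entry limits (heart rate 45 and 100, systolic 155) and three do not (systolic 80, diastolic 100, heart rate 130), so no pattern points to 40. That figure is an eligibility bound, not a safety threshold. A postural diastolic fall of 10 mmHg or more is already tabulated.

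**Conclusion.** The point holds as a narrow defect of definition. As written, 4.5.7 removes a man from every criterion of a parameter once he meets any one of them at baseline. With the Appendix C limits, new values above 130 bpm and below 80 mmHg cannot be counted in men who start above 100 bpm or, in the same position, above 155 mmHg. The effect is limited to the between-arm PCS count and percentage table.

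The number of events is probably very small, because entry limits keep most men inside the upper cut-offs and the systolic case needs a fall of more than 75 mmHg. The figure of 5 to 23 men rests on an assumed 2% to 10% and describes denominators, not lost events. This is a minor improvement, worth making because it is nearly free.

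**What to change.** State in SAP 4.5.7 that the baseline exclusion applies criterion by criterion. A man leaves the <80 row only if he was below 80 at baseline in that position, and the >130 row only if he was above 130 at baseline; the other rows follow the same rule.

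Use the same wording for the laboratory rule in 4.5.6, where Appendix B has limits on both sides for calcium, potassium, sodium, glucose and white cells. A man with low potassium at baseline, for example, should still be able to count as newly high.

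The cost is a sentence in each section and a change to table programming; no new data are needed. The drawback is that denominators will differ by row within a parameter, so each row must print its own.

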## 4.5.8 Electrocardiogram

Electrocardiogram (ECG) parameters collected at study visits are heart rate, PR interval, QRS duration, QT, and QTcF (QT corrected by Fridericia's formula). The actual value, change from baseline value, changes from baseline to worst value during the treatment period, and change from baseline to Month 13 (follow-up visit) will be summarized for quantitative ECG results by treatment group, study visit, and time point (pre-dose and 1-hour post-dose). The overall ECG assessments will be summarized categorically (normal, abnormal without clinical significance, and abnormal with clinical significance) as a shift table by treatment group, study visit, and timepoint. With the exception of change from baseline to the worst post-baseline value during the treatment period, results from unscheduled visits will not be included in the summaries.

Summaries will also be provided for the change from predose values for ECG heart rate, where the predose value is the last value obtained prior to dosing at each visit where ECG is assessed. If a subject has multiple ECG results at a particular visit/time point, the repeat measurement reason will be checked to determine if the first or the last non-missing value will be used for the summary. If the reason for the repeat assessment is abnormal value, then the first value will be used. If the reason is misplacement of the limb lead electrodes, the last value will be used. Results from unscheduled visits will not be included in these descriptive summary tables.

The number (%) of subjects experiencing heart rate increase from pre-dose to post-dose and the number of occurrences per subject will be summarized with various threshold values (ranging from >5 bpm to >40 bpm, with threshold values increasing by 5 bpm). The median, minimum, and maximum heart rate increase (in bpm) will be provided per threshold value. The number of occurrences per subject will be summarized using the median, minimum, and maximum values. All ECG heart rate data, including repeat and unscheduled assessments, will be included in determining the increase from pre-dose in this summary. To evaluate the relationship between age and heart rate increase, the above summary of heart rate increase with various threshold values will also be repeated by treatment and age group (< 65, 65 - < 75, and  $\geq$  75 years).

The number (%) of subjects with the following clinically important QTcF values will be presented by treatment group, visit, and timepoint. Results from repeat/unscheduled visits will be included in shift analyses, as applicable:

- Post-baseline QTcF > 450 msec
- post-baseline QTcF > 480 msec
- post-baseline QTcF > 500 msec
- change from baseline > 30 msec in QTcF
- change from baseline > 60 msec in QTcF
- post-baseline QTcF > 500 msec and change from baseline >60 msec in QTcF

Shift tables from baseline to post-baseline QTcF values using the following categories will be presented for each post-baseline visit and time point. Results from repeat/unscheduled visits will be included in shift analyses, as applicable

- $\leq$  450 msec and > 450 msec
- $\leq 480$  msec and > 480 msec
- $\leq 500$  msec and > 500 msec.

All ECG data will be provided by subject in a data listing. Listings will also be provided for those subjects who have any QTcF values greater than 450 msec, 480 msec, and 500 msec, and those with QTcF change from baseline values >30 msec and >60 msec.

During the COVID-19 pandemic, ECG may be conducted at a subject's home (home visit) by authorized personnel and then be processed and assessed by a central reader. To explore the effect of the COVID-19 pandemic, summaries for ECG parameters will also be presented for the following:

- By region (North America and Europe)
- By subject's study status relative to COVID-19 pandemic onset (subjects who completed or withdrew from the study before 01 March 2020, vs subjects who completed or withdrew from the study on or after 01 March 2020)

### 4.5.9 Concomitant Medications

Medication history and concomitant medications will be coded using the WHO Drug Dictionary. Medications will be tabulated by anatomic therapeutic class (ATC), preferred term (PT), and treatment group. Medications and concomitant medications will be summarized using the Safety population. All recorded medications will be presented in a by-subject listing.

Summary of concomitant medications will include medications taken from the date of the first dose of study medication (Day 1) until 30 days after the last dose of study medication. Medications that did not end prior to the first dose of study medication will be included in the summary.

Prior medications (those with start date prior to the first dose of study medication) will also be summarized by ATC, PT, and treatment group.

If both start date and stop date are missing, the medication will be assumed to occur both prior and concomitantly.

To explore the effect of the COVID-19 pandemic, summaries for the prior medications and concomitant medications will also be presented for the following:

- By region (North America and Europe)
- By subject's study status relative to COVID-19 pandemic onset (subjects who completed or withdrew from the study before 01 March 2020, vs subjects who completed or withdrew from the study on or after 01 March 2020).
- By medication start dates relative to COVID-19 pandemic onset (medications start before 01 March 2020, vs medications start on or after 01 March 2020). For the calculation of percentages, the denominator includes all subjects in the safety population for the relevant treatment group.

# **5 CHANGES FROM THE PROTOCOL-SPECIFIED ANALYSES**

The following changes from the protocol-specified analyses are included in this SAP:

- In Section 1.2.5, a word "Serum" is added to the additional secondary efficacy endpoint "carboxy-terminal cross-linking telopeptide of type I collagen (s-CTX) at 1, 3, 6, and 12 months"
- In Section 1.2.5, the words "12 months" are replaced by "end of treatment" in the additional secondary efficacy endpoint "Proportion of subjects converting from the categories of osteoporosis to osteopenia or to normal at 12 months" to clarify the timepoint at which the endpoint is assessed.
- Section 2.2 defines the Antibody Population
- Section 3.12 defines analysis visit windows for the analyses of BMD, vBMD, and serum markers of bone metabolism (s-PINP and s-CTX) data to determine the assessment that will be used for a given study visit.
- In Section 4.3.1, the primary analysis will use a pattern mixture model (PMM) analysis with multiple imputation using the wash-out imputation method, instead of the protocol-specified ANCOVA model using LOCF technique to impute missing values. The LOCF method has been shown to lead to substantial bias in estimating treatment effects and is no longer recommended by regulatory authorities. While the PMM analysis with wash-out imputation is an appropriate approach to address the possibility of data missing not at random. The PMM analysis with wash-out imputation method was recommended by the FDA in their comment on the primary analysis of this study: *Advice-Information Request IND 73176, dated 05 March 2021*.
- In Section 4.3.1, age is removed from the MMRM and ANCOVA models as a covariate. From previous clinical studies, there is little evidence to suggest that age is associated with the BMD response in subjects who have taken abaloparatide-SC.
- In Section 4.5.3, definitions and summary of AESIs are added. AESIs were not defined in the protocol.
- Additional analyses to evaluate the impact of the COVID-19 pandemic on study conduct were added for safety and efficacy endpoints where applicable.
- The results of antibody analyses will be presented in a separate report.

All other statements in this SAP are enhancements to the statistical considerations described in the protocol.

# Appendix A. Algorithm to Identify Significant Protocol Deviations that Exclude Subjects from the Per-Protocol (PP) Population

A protocol deviation is any change, divergence, or departure from the study design or procedures defined in the protocol. Significant PDs are a subset of PDs that have the potential to impact the effect of the treatment on the subject.

The below algorithm outlines the criteria for identifying significant protocol deviations. Subjects with at least one of these significant protocol deviations will be excluded from the PP population.

- A. Deviations of subject eligibility (Inclusion/Exclusion criteria) that will result in exclusion from PP population:
  - 1. Inclusion Criterion #2: A BMD T-score above the required level.
  - 2. Exclusion Criterion #2: A BMD T-score below the required limit.
  - 3. Exclusion Criterion #1: Presence of abnormalities of the lumbar spine that would prohibit assessment of spinal bone mineral density.
  - 4. Exclusion Criterion #3: Unevaluable hip BMD or subjects who have undergone bilateral hip replacement.
  - 5. Exclusion Criterion #4: Fragility fracture within the 12 months prior to signing of informed consent.
  - 6. Exclusion Criterion #5: History of severe vertebral fracture or > 2 moderate vertebral fractures.
  - 7. Exclusion Criteria #6, #8, and #10: Diseases and treatments affecting the bone strength.
  - 8. Inclusion Criterion #5: Laboratory tests affecting the bone strength
  - 9. Exclusion Criteria #18, #19, #20, #21, #22, #23, #24, #25, and #27. Prior treatment with bone acting agents within the specified time period.
- B. Deviations of study drug administration that will result in exclusion from PP population:
  - 1. The blinding of the study drug was broken during the subject's participation in this study before database lock.
  - 2. Duration of study drug exposure is less than 3 months (90 days)
  - 3. Compliance to study drug administration < 80%
- C. Deviations of efficacy measurements that will result in exclusion from PP population:
  - 1. Lumbar spine BMD is missing at baseline
  - 2. No post-baseline lumbar spine BMD measurements recorded
- D. Other significant protocol deviations
  - 1. Any protocol deviation with potential major impact on the primary efficacy endpoint will exclude a subject from the PP population. This will include subjects taking any prohibited medications during study.

Lab Parameter	Conventional Unit		SI Unit	
	Low	High	Low	High
Hematology				·
Absolute Eosinophils		>5000 cells/mm 		>5.00 10  /L
Absolute Lymphocytes	≤499 cells/mm 		≤0.499 10  /L	
Absolute Neutrophils	≤999 cells/mm 		≤0.999 10  /L	
Hemoglobin	$\leq 10.4 \text{ g/dL} \text{ (male)}$	change from baseline ≥2.1 g/dL	$\leq 104 \text{ g/L} \text{ (male)}$	change from baseline ≥21 g/L
Platelets	≤99000 cells/mm 		≤99 10  /L	
White Blood Cells	$\leq$ 1499 cells/mm 	$\geq$ 20001 cells/mm 	≤1.499 10  /L	≥20.0 10  /L
Coagulation				
Activated Partial Thromboplastin Time		≥1.41*ULN		≥1.41*ULN
Serum Chemistry				
Alanine Aminotransferase		≥5.1*ULN		≥5.1*ULN
Albumin	<2.5 g/dL		<25 g/L	
Alkaline Phosphatase IFCC		≥3.1*ULN		≥3.1*ULN
Aspartate Aminotransferase		≥5.1*ULN		≥5.1*ULN
Bilirubin Total		≥1.51*ULN (with ALT and/or AST>ULN)		≥1.51*ULN (with ALT and/or AST>ULN)
		$\geq$ 2.0*ULN (with normal liver function tests)		≥2.0*ULN (with normal liver function tests)
Calcium	≤7.4 mg/dL	≥11.6 mg/dL	≤1.85 mmol/L	≥2.9 mmol/L
Cholesterol Total		>226 mg/dL		>5.8534 mmol/L
Creatine Kinase		≥3.1*ULN		≥3.1*ULN
Creatinine		$\geq 2.1 \text{ mg/dL}$		$\geq$ 185.64 umol/L
Glucose	$\leq$ 54 mg/dL	>200 mg/dL (random)	$\leq$ 2.997 mmol/L	> 11.1 mmol/L
Potassium	≤3.2 mEq/L	≥5.5 mEq/L	$\leq$ 3.2 mmol/L	≥5.5 mmol/L
Protein Total	<5 g/dL		<50 g/L	
Sodium	≤129 mEq/L	≥148 mEq/L	$\leq 129 \text{ mmol/L}$	≥148 mmol/L
Urine				
Glucose		2+ (≥100 mg/dL)		2+ (≥5.55 mmol/L)
Protein		2+ (≥100 mg/dL)		$2+ (\geq 1.0 \text{ gm/L})$
Blood (microscopic)		>50 rbc/hpf		>50 rbc/hpf
Source: FDA Guidance for Indus and Adolescent Volunteers Enrol	try 2007, Toxicity Gradi led in Preventive Vaccin	ng Scale for Healthy Adult e Clinical Trials		

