6.5. Laboratory Evaluations

6.5.1. Clinical Laboratory Evaluations

Hematology, serum chemistry, and urinalysis will be collected at time points indicated in the Schedule of Assessments and Procedures in Table 3. All clinical laboratory blood and 24-hour urine samples will be sent to a central laboratory for analysis and testing. A list of study clinical laboratory tests is in Table 5.

Hematology	Serum Chemistry	Urinalysis (Dipstick) ^a	Additional Tests
Hemoglobin	Sodium	pH	PTH (1-84) ^b
Hematocrit	Potassium	Glucose	25-hydroxyvitamin D ^b
			1,25-dihydroxy vitamin D ^b
WBC count with	Chloride	Protein	BSAP
differential in absolute			
counts			
RBC count	Inorganic phosphorus	Ketones	Estradiol
MCV	Albumin	Bilirubin	l estosterone ^b
MCHC	Total protein	Blood	SHBG [®]
МСН	Glucose	Urobilinogen	$1SH (13 \text{ and Free } 14)^c$
Platelet count	BUN	Specific gravity	
	Creatinine	Nitrite	
	Uric acid	Leukocytes	
	AST		
	ALT		
	GGT		
	СРК		
	Alkaline phosphatase		
	Total bilirubin		
	LDH		
	Total Cholesterol		
	Triglycerides		
	Total calcium		

Table 5: Clinical Laboratory Tests

a. Clinic only, if required by PI send to central lab for microscopy

b. Only required at Screening and Visit 8 or early termination (Month 12 visit)

c. Only required at Screening. Reflex testing for T3 and Free T4 will be performed by the central laboratory if TSH is outside the normal limits. Reflex testing for bone-specific alkaline phosphatase will be performed by the central laboratory if serum alkaline phosphatase is outside the normal limits.

ALT = alanine aminotransferase; AST = Aspartate aminotransferase; BSAP = bone-specific alkaline phosphatase; BUN = blood urea nitrogen; CPK = Creatine phosphokinase; GGT = gamma-glutamyl transpeptidase; LDH = lactate dehydrogenase; MCH = mean corpuscular hemoglobin; MCHC = mean corpuscular hemoglobin concentration; MCV = Mean corpuscular volume; PTH = parathyroid hormone; RBC = red blood cell; SHBG = sex hormone binding globulin; TSH = thyroid stimulating hormone; WBC = white blood cell

In the event of medically significant, unexplained, or abnormal clinical laboratory test values, the test(s) should be repeated and followed up until the results have returned to within the normal range or an adequate explanation for the abnormality is found. Clinically significant changes in laboratory tests that occur during the course of the study are to be reported as AEs.

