## 4.5.6 Laboratory Data

Clinical laboratory values will be provided in conventional units and in standard international (SI) units by the central laboratory.

Summaries of laboratory data using descriptive statistics by treatment group and study visit will be presented based on the SI units, including absolute results and changes from baseline. This includes serum chemistry, hematology, coagulation, hormones (including total testosterone, estradiol, SHBG, and PTH), 25-hydroxyvitamin D, 1,25-dihydroxy vitamin D, and urinalysis (for quantitative urinalysis assays). In the event of repeat assessments during a visit time point, the last non-missing value per study day/time will be used in the summary statistics. In the event of duplicate assessments at a visit time point, the worst value per study day/time will be used in the summary statistics. Results from unscheduled visits will not be included in the summaries.

Shift analyses of laboratory data from baseline to the worst post-baseline value and from baseline to Month 12/ET (Visit 8) will be performed by treatment group. Results for serum chemistry,

hematology, coagulation, and urinalysis will be presented by category (above normal limit, within normal limit, below normal limit). For shift tables from baseline to worst post-baseline value, and for baseline to Month 12, percentages will only be calculated based on the number of subjects with valid data for baseline and post-baseline; subjects who are missing either assessment will not be included in the percentage calculation (numerator or denominator). Results from unscheduled visits will be included in the shift analyses, as applicable.

To explore the effect of the COVID-19 pandemic, summaries of all laboratory parameters will also be presented for the following:

- By region (North America and Europe)
- By subject's study status relative to COVID-19 pandemic onset (subjects who completed or withdrew from the study before 01 March 2020, vs subjects who completed or withdrew from the study on or after 01 March 2020)

Any laboratory parameter value that is provided as "< *numeric value*" or "> *numeric value*" will be imputed as the *numeric value* in all summary tables and analyses; but will be shown with the actual result in the listings.

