## Potentially Clinically Significant Laboratory Values

Criteria for determining values of laboratory tests that are considered Potentially Clinically Significant (PCS) are in Appendix B of this SAP. The number (%) of subjects with at least 1 post-baseline PCS values who did not have PCS values at baseline will be presented for each laboratory parameter. Results from unscheduled visits will be included in identification of subjects with post-baseline PCS values, as applicable. For the calculation of the percentages of subjects, the denominator will be based on the number of subjects who had no PCS values at baseline and had at least one post-baseline assessment for the specific laboratory parameter of interest. The numerator will be based on the number of subjects from the denominator who had at least one PCS value post-baseline for the specific laboratory parameter of subjects with any PCS values will be provided.

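### SAP Appendix B gives no direction for the hemoglobin change criterion and places it under High; read as placed, a fall is flagged only once hemoglobin reaches 10.4 g/dL or less.

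*SAP*

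**What the plan says.** The table in SAP Appendix B has a Low and a High column for conventional units and the same pair for SI units. In the hemoglobin row:

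- Low: an absolute value of 10.4 g/dL or less for males (104 g/L or less).
- High: "change from baseline ≥2.1 g/dL" in conventional units and "change from baseline ≥21 g/L" in SI units.

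The row contains no plus or minus sign, no word for increase or decrease, and no reference to absolute change.

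SAP Section 4.5.6 explains how the criteria are used. For each parameter it counts subjects with at least one post-baseline PCS value "who did not have PCS values at baseline". For the percentage, "the denominator will be based on the number of subjects who had no PCS values at baseline" and who had a post-baseline assessment. Unscheduled results are included, and a listing of subjects with PCS values accompanies the table. The section says nothing about the direction of the hemoglobin change.

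**The concern.** A criterion based on change from the subject's own baseline is useful because it picks up a large individual shift before an absolute limit is crossed. For hemoglobin the absolute limit in the table is on the low side, while the change criterion stands on the high side. Programmed as post-baseline minus baseline of at least +2.1 g/dL, it would flag every rise of that size and no fall. A man who lost much more than 2.1 g/dL but stayed above 10.4 g/dL would then be missing from both the PCS count and the PCS listing.

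At stake is whether the PCS table gives a usable comparison between arms of large individual falls in hemoglobin. No efficacy endpoint, significance level or power figure depends on it.

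**Working it through.** **Inputs.** From SAP Appendix B: the absolute limit (10.4 g/dL or less) and the change threshold (2.1 g/dL or more). Baseline hemoglobin is not given. Protocol Section 4.1, criterion 8, requires only that "The subject has no clinically significant abnormality of serum hemoglobin" be present, with no numeric limit. Baselines of 12.0 to 17.0 g/dL are therefore an assumption. Values are taken to be reported to 0.1 g/dL (1 g/L).

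**The plan's own figures.** Multiplying g/dL by 10 gives g/L: 10.4 × 10 = 104 and 2.1 × 10 = 21. Both agree with the SI block. The change criterion is under High in both blocks, so a slip of one column in a single block is an unlikely explanation.

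**Reading A: rise only (post-baseline minus baseline ≥ +2.1, or value ≤ 10.4).** The lowest value not flagged is 10.5, so the largest unflagged fall is baseline − 10.5.

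| Assumed baseline (g/dL) | Largest unflagged fall (g/dL) |
|---|---|
| 12.0 | 12.0 − 10.5 = 1.5 |
| 12.6 | 12.6 − 10.5 = 2.1 |
| 13.5 | 13.5 − 10.5 = 3.0 |
| 14.5 | 14.5 − 10.5 = 4.0 |
| 14.6 | 14.6 − 10.5 = 4.1 |
| 15.0 | 15.0 − 10.5 = 4.5 |
| 17.0 | 17.0 − 10.5 = 6.5 |

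An unflagged fall of at least 2.1 thus needs a baseline of 12.6 or more, and one above 4 needs 14.6 or more. At every baseline the largest unflagged rise is 2.0.

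**Reading B: either direction (absolute change ≥ 2.1, or value ≤ 10.4).** The largest unflagged fall is 2.0 at any baseline of 12.5 or more and 1.5 at 12.0. No fall of 2.1 or more escapes, but a rise and a fall of the same size meet the same criterion.

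**Which reading does the SAP suggest?** Three features point to Reading A. The criterion is in the High column, where the other entries flag high values. Section 4.5.8 lists unsigned QTcF changes above 30 and 60 msec beside the limits for prolonged QTcF, so unsigned change there means an increase. Section 4.5.7 names a decrease explicitly when it defines orthostatic hypotension. On the other side, Sections 4.5.7 and 4.5.8 also write increase explicitly for heart rate, so the SAP's usage is not uniform. The text leans towards Reading A without settling it.

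**The case against.** The strongest reply is that an unsigned change is ambiguous and not wrong. Reading B is possible, and under it no fall of 2.1 g/dL or more is missed. That stands, and it is why the point cannot be put as a plain statement that falls are not counted. It does not make the row adequate, because two programmers could code it differently and Reading B would mix rises with falls under High.

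A reader might infer that a man could lose more than 4 g/dL without the loss being treated as clinically significant. The documents do not support that. The figure needs Reading A together with a baseline of at least 14.6 g/dL, which they do not supply. The table also defines potentially significant values, a programmed screen; clinical significance is for the investigator to judge. Protocol Section 6.5.1 says: "Clinically significant changes in laboratory tests that occur during the course of the study are to be reported as AEs". Protocol Section 7.1.1 extends this to shifts within the normal range that the investigator considers clinically important.

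Other outputs would also show falls. SAP Section 4.5.6 plans hematology change summaries by visit, and Section 3.2 includes the minimum and maximum. Section 4.5.6 adds "Shift analyses of laboratory data from baseline to the worst post-baseline value", with unscheduled results included, and listings of all values with high and low indicators. These limit the harm but do not replace the PCS count:

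- The change summaries describe groups and leave out unscheduled visits.
- The shift tables have three categories, so a large fall within the normal range does not appear, and one that crosses the limit looks the same as a trivial crossing.
- Adverse event reporting depends on judgement, with no uniform threshold.
- Listings are not counted by arm.

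Finally, Appendix B cites an external grading scale, which was not consulted here. The intended direction therefore has to be confirmed by the sponsor and cannot be inferred from the row alone.

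**Conclusion.** The hemoglobin change criterion is inadequately specified, and its placement invites a rise-only program. If it is coded that way, a fall is a PCS value only at 10.4 g/dL or less, and the largest unflagged fall is the baseline minus 10.5 g/dL: 3.0 at an assumed baseline of 13.5 and 4.5 at 15.0. If it is coded in either direction, no fall of 2.1 g/dL or more is lost, but falls cannot be told apart from rises.

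The effect is confined to one row of a descriptive PCS table and its listing. SAP Section 4.5 plans no formal testing of safety endpoints unless otherwise specified, and the adverse events of special interest in Section 4.5.3 do not name hemoglobin or anemia. The correction is still worth making, because no other planned output counts large individual falls by arm against a uniform threshold.

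**What to change.** Before programming, check the direction of the criterion against the grading scale cited in Appendix B, then state it in the hemoglobin row so that falls are counted:

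- Low: keep the absolute limit and add a decrease from baseline of at least 2.1 g/dL (at least 21 g/L).
- High: if a rise is also of interest, show it as a separately labelled increase from baseline of at least 2.1 g/dL (at least 21 g/L); otherwise leave the cell empty.

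Report decreases and increases as separate counts. The cost is one table row and a line of code, with no new data. Making the change before unblinding avoids choosing a safety definition after the results are known.
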